	
 1. EGFR mutated (common mutations), TKI-naïve advanced NSCLC treated with Gi(1)otrif[®] as the first-line treatment for NSCLC within the approved label will be included 2. Patients treated within clinical trials are excluded 3. Patients still on treatment with Gi(1)otrif[®] will be excluded unless treatment period is ≥ 6 months
Variables:	
Primary outcomes:
 
Safety outcomes:
 
Percentage of subjects with adverse drug reactions by severity class
 
Effectiveness outcomes:
 
Time on treatment with Gi(1)otrif[®]
 
Time to progression with Gi(1)otrif[®]

Data sources:	NIS based on existing data from medical records of patients.
Study size:	At least 200 patients. ≥ 200 patients are planned based on feasibility aspects and assumptions.
Data analysis:	
Safety data will be analysed in a descriptive manner. Incidence and severity of adverse drug reactions will be summarized and displayed. For patients who have dose modifications, frequency and severity of the most common AEs pre- and post-dose modification will be summarized and displayed.
 
For effectiveness analysis, both time on treatment and time to progression will be estimated using Kaplan-Meier method, and the median along with two-sided 95% CI will be displayed (use the Greenwood's formula for estimation of standard errors). Log-rank test will be applied to compare between patients with and without dose modifications.

Milestones:	
Start of data collection in May 2016
 
End of data collection in December 2016
 
Final report of study results expected in March 2017

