Afatinib 40 mg/day (oral) is approved for the treatment of patients with advanced EGFRm+ NSCLC. Dose adjustments are recommended based on pre-defined tolerability criteria. A post-hoc analyses of the effects of afatinib dose reduction on adverse events (AEs), pharmacokinetics (PK) and PFS in the phase III LUX-Lung 3 trial showed that dose reductions occurred in 53% (122/229) of patients; the majority (86%) within the first 6 months of treatment. In patients who dose reduced, decreases in the incidences of drug-related all grade (grade \geq 3) AEs were 99.2% (20.5%) to 46.7% (4.1%) for diarrhea, 88.5% (26.2%) to 38.5% (3.3%) for rash/acne, 77.0% (12.3%) to 27.9% (0%) for stomatitis, and 44.3% (16.4%) to 36.9% (4.9%) for nail effects. Dose reductions tended to be more common in female patients, older patients, patients of Eastern Asian ethnicity, and patients with lower body weight. Dose reduction was more likely in patients with higher plasma concentrations of afatinib. On Day 43, patients who dose reduced to 30 mg \geq 4 days previously (n=38) had geometric mean plasma afatinib concentrations of 24.4 ng/mL, vs 23.7 ng/mL in patients who remained on the 40 mg dose (n=126). Median PFS was 11.3 months in patients who dose reduced during the first 6 months of treatment, vs 11.0 months in patients who did not (HR=1.25 [95% CI, 0.91–1.72]). [ASCO 2015, Yang et al, # 8073] ([P15-05676](#)).

Post-hoc analyses from LUX-Lung 3 suggest that tolerability-guided dose adjustment of afatinib is an effective measure to reduce treatment-related AEs without affecting therapeutic efficacy:

- The frequency and severity of treatment-related AEs was lower following dose reduction
- Tolerability-guided dose modification reduced the inter-patient variability of afatinib exposure, while maintaining efficacious plasma levels
- Efficacy outcomes were similar in patients who dose reduced due to AEs versus those who did not

This real-world data (RWD) study will help to understand if dose modifications are done similar as in LUX-Lung 3 trial and if the outcome on safety and effectiveness are as in trial settings.

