9.7 DATA ANALYSIS

9.7.1 Main analysis

All collected data will be analysed separately for patients starting with 40mg and \leq 30mg. Although due to anticipated low sample size in patients starting with \leq 30mg, it will be mainly for exploratory purpose. Baseline demographics will be analysed with descriptive statistics (N, median, mean, 25%, 75% percentile, SD) and compared descriptively between patients who have dose modifications within the first 6 months of Gi(l)otrif[®] treatment and those who do not. All the demographics, safety and efficacy data from this study in real-world setting will be compared with data from LUX-Lung 3 trial in descriptive manner.

Analysis of Safety:

[figure not shown]
Safety analysis will include all patients treated with Gi(l)otrif[®] and be descriptive in nature. Incidence and severity of ADRs according to Common Terminology Criteria for Adverse Events (CTCAE) criteria (version 4.0) ([R15-5988](#)) when available will be summarized and displayed in number/percentage. For patients who had Gi(l)otrif[®] dose modifications within the first 6 months of Gi(l)otrif[®] treatment, frequency and severity of the common ADRs pre- and post-dose modification will be analysed (\geq 40mg vs $<$ 40mg; and \geq 30mg vs $<$ 30mg). Missing or incomplete ADR dates will be imputed according to BI internal SOPs.

Analysis of Effectiveness:

Effectiveness analysis will include all patients treated with Gi(l)otrif[®]. Time on treatment is from the date of first dose of Gi(l)otrif[®] treatment to the date of last dose of Gi(l)otrif[®] treatment. Time to progression is from the date of first dose of Gi(l)otrif[®] treatment to the earliest date of documented progression (clinical, radiographic or both clinical/radiographic progression) or death. Time on treatment and time to progression will be estimated using Kaplan-Meier method, and the median along with two-sided 95% CI will be displayed (use the Greenwood's formula for estimation of standard errors). Log-rank test will be applied to compare between patients with and without dose modifications. Time on treatment and time to progression will be compared between patients who dose reduced to $<$ 40 mg within the first 6 months of Gi(l)otrif[®] treatment and those who remained on Gi(l)otrif[®] 40 mg once daily. This is in analogy to the analysis made on LUX-Lung 3 where a cut-off of 6 months was used as most dose reductions occur during this time.

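### The before/after ADR table is limited to dose modifications in the first 6 months, but the abstract sets no limit and the quoted LUX-Lung 3 figures cover all 122 reducers

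*Protocol*

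**What the plan says.** The Analysis of Safety paragraph in protocol section 9.7.1 defines the before/after ADR population with "For patients who had Gi(l)otrif[®] dose modifications within the first 6 months of Gi(l)otrif[®] treatment". The abstract (section 4, Data analysis) plans the same summary without a window: "For patients who have dose modifications, frequency and severity of the most common AEs pre- and post-dose modification will be summarized and displayed".

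Section 9.7.1 also states that "All the demographics, safety and efficacy data from this study in real-world setting will be compared with data from LUX-Lung 3 trial", descriptively. It gives a reason for the 6-month cut-off only in the effectiveness paragraph: "This is in analogy to the analysis made on LUX-Lung 3 where a cut-off of 6 months was used".

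Section 7 describes the LUX-Lung 3 post-hoc analysis. It reports that "dose reductions occurred in 53% (122/229) of patients; the majority (86%) within the first 6 months of treatment". The before/after adverse-event rates follow directly, introduced by "In patients who dose reduced, decreases in the incidences of drug-related all grade", with no time limit and no denominator printed beside them. Section 7 uses the 6-month split only for median PFS.

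The SAP text available covers derived variables and date imputation. It does not define the before/after population, so it does not settle the matter.

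**The concern.** The effect of dose modification on ADR frequency and severity, set descriptively against LUX-Lung 3, is part of the primary objective (section 8). A descriptive comparison has no adjustment step, so matching the population definitions is its main protection. Here the real-world table would hold early modifiers only, while the only LUX-Lung 3 rates supplied appear to hold early and late reducers together. Part of any difference could then reflect who was admitted to the table.

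The reason given for the cut-off does not carry over to safety. A comparison of time to event between reducers and non-reducers needs a rule for classifying patients. A within-patient before/after table is anchored on each patient's own modification date and does not depend on such a rule. The abstract and section 9.7.1 also disagree, so two analysts could build different tables from the same protocol.

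**Working it through.** **Inputs.** From section 7: 122 reducers of 229 patients, 86% of them within 6 months, and the 16 before/after percentages, "99.2% (20.5%) to 46.7% (4.1%) for diarrhea, 88.5% (26.2%) to 38.5% (3.3%) for rash/acne" and "77.0% (12.3%) to 27.9% (0%) for stomatitis, and 44.3% (16.4%) to 36.9% (4.9%) for nail effects" (grade 3 or higher in brackets). From section 9.5: 200 patients, 25-30% expected to start on a lower dose.

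**1. Reproduce the stated rate.** 122/229 = 53.3%, which matches the printed 53%.

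**2. Early and late reducers.** A count that rounds to 86% of 122 must lie between 0.855 × 122 = 104.3 and 0.865 × 122 = 105.5, so it is 105. Late reducers: 122 − 105 = 17, or 14%.

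**3. Identify the denominator of the adverse-event rates.** For each candidate N, count how many of the 16 percentages equal a whole number k divided by N, to one decimal. With N = 122:

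| Event | Before, all grades | Before, grade ≥3 | After, all grades | After, grade ≥3 |
|---|---|---|---|---|
| Diarrhea | 121 (99.2%) | 25 (20.5%) | 57 (46.7%) | 5 (4.1%) |
| Rash/acne | 108 (88.5%) | 32 (26.2%) | 47 (38.5%) | 4 (3.3%) |
| Stomatitis | 94 (77.0%) | 15 (12.3%) | 34 (27.9%) | 0 (0%) |
| Nail effects | 54 (44.3%) | 20 (16.4%) | 45 (36.9%) | 6 (4.9%) |

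All 16 fit. With N = 105 only 2 fit: 49/105 = 46.7% and 0/105 = 0%. Among the denominators tried (95 to 129, and 229), none other than 122 fits more than 5. The rates therefore describe all reducers, not early reducers.

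**4. What an early-only rate could be.** The documents do not give it. If x of the 122 had the event, the early-only rate lies between (x − 17)/105 and x/105 for the four all-grade rates after reduction:

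- Diarrhea: 40/105 to 57/105 = 38.1% to 54.3% (printed 46.7%)
- Rash/acne: 30/105 to 47/105 = 28.6% to 44.8% (printed 38.5%)
- Stomatitis: 17/105 to 34/105 = 16.2% to 32.4% (printed 27.9%)
- Nail effects: 28/105 to 45/105 = 26.7% to 42.9% (printed 36.9%)

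These are extreme bounds, not expected shifts. They show that a matching early-only benchmark cannot be recovered from the printed rates.

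**5. Patients left out of the planned table.** Assume the LUX-Lung 3 reduction rate and its 14% late share apply. Starters on 40 mg: 200 × 0.70 = 140 to 200 × 0.75 = 150.

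| Start on 40 mg | Reducers (× 122/229) | Within 6 months (× 0.86) | Left out (× 0.14) |
|---|---|---|---|
| 140 | 74.6 | 64.1 | 10.4 |
| 150 | 79.9 | 68.7 | 11.2 |
| 200 (upper case) | 106.6 | 91.6 | 14.9 |

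**The case against.** The strongest reply is that section 9.7.1 never names the LUX-Lung 3 figures to be used. LUX-Lung 3 is the sponsor's own trial (listed in section 2 under a BI trial number), so a matching 6-month cut is possible. This stands in part: a reader might infer that the plan commits to the 122-patient rates, and it does not say so. But no re-cut is planned in the documents, and section 7 holds the only such rates they contain.

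Second, the window has a use. Section 9.2.1 admits patients still on treatment only after at least 6 months, so the first 6 months is the period in which modification status can be established for every patient. An any-time definition lets the late share depend on length of follow-up. This is a fair reason to keep the 6-month table as support and to report follow-up, but it does not make that table the counterpart of the 122-patient rates.

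Third, the effect is likely to be modest. An early-only rate differs from the all-reducer rate by 0.14 × (early rate − late rate). If the two groups differed by 20 points (an assumption), the shift would be 0.14 × 20 = 2.8 points. With about 67 early reducers, the 95% half-width around 46.7% is 1.96 × √(0.467 × 0.533/67), about 12 points. This stands. The case for change rests on avoidable inconsistency and low cost, not on a large expected distortion.

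**Conclusion.** The concern holds as a mismatch of definitions. Section 9.7.1 and the abstract disagree on who enters the before/after ADR table. The section 9.7.1 version does not match the only LUX-Lung 3 rates in the documents, whose denominator is 122. About 14% of reducers would be left out: 10-11 of 75-80, or about 15 of 107 if all 200 start on 40 mg. Those counts assume that LUX-Lung 3's reduction rate and timing carry over to routine practice.

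Two stronger readings are not supported. A reader might infer that late reducers vanish from the safety analysis. They do not: the primary safety outcome, ADRs by severity class (section 9.3.2.1), is summarised over all treated patients. A reader might also infer a bias in a known direction, for example because late reducers have later or cumulative reactions. The documents say nothing about that. The small fall in nail effects (44.3% to 36.9%) shows how much they changed after reduction, not when they arose or in whom. The direction cannot be determined.

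**What to change.** Reconcile the abstract and section 9.7.1, and state in both and in the SAP:

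- The before/after ADR table includes all patients who reduced dose at any time on treatment. This is the table set beside the 122-patient LUX-Lung 3 rates.
- The first-6-months subset is kept as a supportive table. If it is compared with LUX-Lung 3, the comparator is a matching 6-month cut of the sponsor's own LUX-Lung 3 data.
- Length of follow-up is reported alongside, because the share of late reducers depends on it.

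The wording should say reductions for this table. Section 9.7.1 says modifications, which can include escalation, while the LUX-Lung 3 rates concern reductions. That is a separate mismatch, and removing the time limit alone would not cure it.

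The cost is a wording change and one extra table. Section 9.3 already collects dose-modification dates and ADRs from first dose to last dose or end of data collection, so no new data are needed. A 6-month cut of LUX-Lung 3 adds work only if the subset comparison is wanted.

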9. RESEARCH METHODS

9.1 STUDY DESIGN

This is a non-interventional, multi-country, multi-site study based on existing data from medical records of patients treated with Gi(l)otrif[®] as part of the routine treatment according to the approved label.

Key study outcomes are:

- Effects of Gi(l)otrif[®] dose reduction on frequency of ADRs, and time on treatment, time to progression
- Proportion of patients starting with modified Gi(l)otrif[®] dose and the underlying reason(s)

Data on diagnosis, gender, date of birth, ethnicity, body weight and height, Eastern Cooperative Oncology Group performance score (ECOG) ([R14-0080](#)), EGFR mutational subgroup (Del19/L858R), starting dose of Gi(l)otrif[®], start date of Gi(l)otrif[®] treatment, dose modifications with date, ADRs, concomitant medications (limited to medication for management of diarrhea, skin effects, mucositis/stomatitis as dichotomous variables (e.g. received anti-diarrhea medication yes/no), reason for dose modification of Gi(l)otrif[®], treatment duration of Gi(l)otrif[®], time to progression and type of progression (clinical, radiographic or both clinical/radiographic progression) will be collected from patients medical records by investigators.

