9.3.1 Exposures

Patients were/are treated with Gi(l)otrif[®] 50mg, 40mg, 30mg, 20mg tablet once daily as indicated in the approved labels of Gi(l)otrif[®].

The recommended starting dose of Gi(l)otrif[®] is 40mg once daily. A modified starting dose of Gi(l)otrif[®] per objective would be considered as any other dose different than 40mg once daily.

The Summaries of Product Characteristics on Gi(l)otrif[®] is contained in the NIS ISF in the “Summary of Product Characteristics” section.

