9.5 STUDY SIZE

The post-hoc analysis of LUX-Lung 3 providing the rationale for this study was based on 229 patients with 53% patients experiencing dose reduction. With a sample size of 200 we would be in the same range as in the LUX-Lung 3 analysis which provided robust data. It will be sufficient to analyse the effects of dose modification on patients' safety and effectiveness and to compare it with data from LUX-Lung 3 trial descriptively.

Based on feedback from physicians we expect 25-30% patients starting with a lower dose.

There will be around 50 patients starting with a modified dose, and around half of them with further de-/escalation. This is a sufficient sample size to get some impression on the reasons of a modified starting dose in real-world setting.

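### The 30 mg pre/post ADR contrast counts 40 mg time as the pre period for 40 mg starters who reach 20 mg, and the plan leaves the direction of dose change undefined

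*Protocol*

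**What the plan says.** Protocol 9.7.1 (Analysis of Safety) takes patients with a dose modification in the first 6 months and states that "frequency and severity of the common ADRs pre- and post-dose modification will be analysed". The bands are given as "\geq 40mg vs $<$ 40mg; and \geq 30mg vs $<$ 30mg". The same section opens by saying "All collected data will be analysed separately for patients starting with 40mg and" those starting at 30 mg or less, and adds that for the low starters "it will be mainly for exploratory purpose".

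Protocol 9.3.1 describes treatment with "50mg, 40mg, 30mg, 20mg tablet once daily as indicated in the approved labels", so the band at or above 30 mg spans three dose levels.

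The wording on direction differs between sections. The key study outcome in Protocol 9.1 is the effect of "dose reduction on frequency of ADRs, and time on treatment, time to progression". Section 9.7.1 speaks of modifications in its safety analysis. Section 9.5 expects movement both ways: "There will be around 50 patients starting with a modified dose, and around half of them with further de-/escalation".

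The SAP text supplied defines age, drug-related AE, time on treatment, time to progression and the imputation of AE onset dates. It gives no rule for dose periods, repeated changes or direction of change.

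**The concern.** A pre/post contrast at a dose step should compare the period just before the step with the period just after it. A band that collects everything at or above 30 mg does not do this for a patient who came down from 40 mg. The 40 mg period, including the ADRs that led to the first reduction, sits on the pre side of the second contrast.

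The primary objective is the effect of dose modification on the frequency and severity of ADRs, and these percentages are the whole safety result. No model follows that could correct the contrast. A reader could take the 30 mg table as evidence that 20 mg is better tolerated than 30 mg when it shows no such thing.

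The second difficulty is direction. If a dose goes up across a cut, the earlier period is in the lower band. A programmer must then choose between time order and band order, and the two choices give different tables.

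**Working it through.** **Inputs.** Dose levels are from Protocol 9.3.1, cuts and starting-dose groups from 9.7.1, and expected numbers from 9.5. LUX-Lung 3 rates are from Section 7: diarrhea "99.2% (20.5%) to 46.7% (4.1%) for diarrhea", all grades with grade 3 or higher in brackets.

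**1. The plan's own figures.** 122/229 = 53.3%, printed as 53%. The diarrhea rates match whole counts out of 122 reduced patients: 121/122 = 99.2%, 57/122 = 46.7%, 25/122 = 20.5%, 5/122 = 4.1%. The descriptive ADR contrast has no power figure to reproduce.

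**2. Sorting dose sequences into the stated bands.**

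| Sequence (mg) | ≥40 | <40 | ≥30 | <30 |
|---|---|---|---|---|
| 40→30 | 40 | 30 | 40, 30 | none |
| 40→30→20 | 40 | 30, 20 | **40, 30** | 20 |
| 40→20 | 40 | 20 | **40** | 20 |
| 30→20 | none | 30, 20 | 30 | 20 |
| 30→40 | 40 (later) | 30 (earlier) | 30, 40 | none |
| 20→30 | none | 20, 30 | 30 (later) | 20 (earlier) |
| 40→30→40 | 40 (first and last) | 30 | 40, 30, 40 | none |
| 40→50 | 40, 50 | none | 40, 50 | none |

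The bold cells show the carry-over. A 40→20 patient enters the 30 mg contrast with no 30 mg exposure at all. A 30→20 patient gives a clean comparison.

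**3. Size of the carry-over.** Let p40, p30 and p20 be the proportions with the ADR in each period.

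- Proportion in the upper band: at least max(p40, p30), at most min(100%, p40 + p30).
- Fall shown: upper-band proportion − p20. True second-step fall: p30 − p20.
- Overstatement: upper-band proportion − p30, so at least p40 − p30 when p40 exceeds p30. The 20 mg rate does not matter.

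Assume that p40 is the LUX-Lung 3 pre-reduction rate and that p30 = p20 = the post-reduction rate, so the true second-step fall is 0:

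- Diarrhea, all grades: lower limit 99.2 − 46.7 = 52.5 points; upper limit 100 − 46.7 = 53.3.
- Diarrhea, grade 3 or higher: lower limit 20.5 − 4.1 = 16.4 points; upper limit (20.5 + 4.1) − 4.1 = 20.5.
- Nail effects, all grades: lower limit 44.3 − 36.9 = 7.4 points, so the size depends strongly on the ADR.
- If the 30 mg diarrhea rate were instead 80%, the overstatement would be at least 99.2 − 80 = 19.2 points.

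**4. How many patients.** With 25–30% of 200 starting lower, 50–60 are low starters and 140–150 start at 40 mg. At LUX-Lung 3 rates, 140 × 0.53 × 0.86 = 63.8 to 150 × 0.53 × 0.86 = 68.4 of the latter reduce within 6 months. The documents do not say how many go on to 20 mg.

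**5. Direction.** About half of the low starters (25–30) are expected to change dose again, with no up/down split. Suppose a share f of a time-ordered comparison were increases with mirrored rates. The 52.5-point diarrhea difference would become 52.5 × (1 − 2f): 42.0 at f = 10%, 26.3 at 25%, 0 at 50%. The documents give no value for f, and it could be 0.

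**The case against.** The strongest reply starts from the planned split by starting dose. Two groups and two cuts suggest a natural pairing: the 40 mg cut for 40 mg starters and the 30 mg cut for those starting at 30 mg or less. On that reading the second contrast is 30 mg against 20 mg, except in low starters who were raised to 40 mg, and the carry-over largely disappears. The pairing is compatible with Section 9.7.1, but the section does not state it; it says that all data are analysed in both groups. The literal carry-over therefore remains.

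On direction, the bands run from higher to lower dose and Section 9.1 names reduction, so reductions may be all that was meant. A 40-to-50 mg change crosses neither cut, and a table headed by dose band can still be read as higher against lower dose. This stands in part. A reader might infer that increases are definitely pooled with reductions. That would be an inference from silence, and within the planned split it would mainly concern the exploratory low starters plus re-escalations.

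A 40-to-30 mg patient gives no contrast at the 30 mg cut, but this is not a defect, because that patient is captured at the 40 mg cut.

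Finally, the protocol's table of contents has a blacked-out heading after 9.7.1, and the SAP announces tables that are not in the text supplied. A rule may exist there. The point is limited to the visible text.

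**Conclusion.** The point holds with limited scope. As written, the 30 mg contrast attributes to the step below 30 mg a fall that may already have occurred at 30 mg, in 40 mg starters who reach 20 mg. For increases across a cut, the pre/post order and the band order conflict.

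The 52.5-point and 16.4-point figures are lower limits under two assumptions: these patients have the rates seen in all 122 reduced LUX-Lung 3 patients, and 30 mg and 20 mg are equally tolerated. They are illustrations and do not forecast the study's result.

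A reader might conclude that the whole pre/post safety comparison, including the comparison with LUX-Lung 3, is distorted. The documents do not support that. The upper side of the 40 mg contrast in 40 mg starters, which parallels the LUX-Lung 3 figures, contains no time from an earlier dose step. The analysis is descriptive, so no error rate or power changes. The gap should be closed before the tables are programmed.

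**What to change.** In the analysis plan, within each starting-dose group:

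- Define the contrasts by consecutive dose periods: the 40 mg period against the 30 mg period for one step, and the 30 mg period only against the 20 mg period for the next.
- Show direct 40-to-20 mg changes in a table of their own.
- Restrict the pre/post tables set beside LUX-Lung 3 to reductions.
- Tabulate increases, including re-escalations, separately, with the earlier lower dose as pre and the later higher dose as post.
- Print the number of patients in every contrast.

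The cost is wording and table specifications. Doses and modification dates are already on the list of collected variables in Protocol 9.3. The drawback is that the second-step and increase tables will be small and can only be descriptive.

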8. RESEARCH QUESTION AND OBJECTIVES

Research objective:

Data from real-world will help to understand if dose modifications are done similar as in LUX-Lung 3 trial and if the outcome on safety and effectiveness are as in trial settings. Furthermore, data on modified starting doses, the underlying reasons and effects on safety and outcome are needed.

Primary objective:

To assess the effects of Gi(1)otrif[®] dose modification on the frequency and severity of adverse drug reactions (ADRs), time on treatment and time to progression with Gi(1)otrif[®] in real-world setting and compare with data from LUX-Lung 3 trial in a descriptive manner.

Secondary objective:

To obtain information on frequency and reasons for a modified starting dose of Gi(1)otrif[®] in real-world setting.

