9.3 VARIABLES

Data will be documented from the date of first dose of Gi(l)otrif[®] treatment until the date of last dose of Gi(l)otrif[®] treatment or end of data collection whichever occurs first.

During the data collection period, the following data will be collected from medical records in an eCRF by investigators during the study:

- Informed consent
- Diagnosis
- Demographics (gender, date of birth, ethnicity)
- Body weight and height at start of Gi(l)otrif[®] treatment
- ECOG performance score at start of Gi(l)otrif[®] treatment
- EGFR mutational subgroup (Del19/L858R)
- Starting dose of Gi(l)otrif[®]
- Start date of Gi(l)otrif[®] treatment
- End date of Gi(l)otrif[®] treatment
- Gi(l)otrif[®] dose modification(s) and date(s)
- ADRs
- Concomitant medications (limited to medication for management of diarrhea, skin effects, mucositis/stomatitis as dichotomous variables (e.g. received anti-diarrhea medication yes/no))
- Reason for dose modification(s)
- Date of progression
- Type of progression:
 - a. clinical
 - b. radiographic
 - c. both clinical/radiographic progression

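### The pre/post-modification ADR percentages can rise or fall with no dose effect; exposure-adjusted sensitivity tables are a cheap improvement

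*Protocol*

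**What the plan says.** The primary objective (Protocol section 8) is to assess the effects of "dose modification on the frequency and severity of adverse drug reactions (ADRs), time on treatment and time to progression".

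For safety, section 9.7.1 plans that in patients modified within the first 6 months "frequency and severity of the common ADRs pre- and post-dose modification will be analysed", split at 40 mg and at 30 mg. The same paragraph says that ADR incidence and severity "will be summarized and displayed in number/percentage". No other scale is named for the pre/post comparison.

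Section 7 explains why doses change: "Dose adjustments are recommended based on pre-defined tolerability criteria". It also gives the precedent, the LUX-Lung 3 post-hoc analysis, with the conclusion "The frequency and severity of treatment-related AEs was lower following dose reduction".

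Section 9.3 collects the start and end dates of treatment, each modification with its date and reason, and the ADRs. Data run from first dose to last dose or the end of data collection.

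The visible text does not define the two periods, derive exposure in each, or say how to count the ADR that prompted the change or an ADR still ongoing at the change. ENCePP checklist item 5.3, on exposure by time windows, is answered No. The limitations and bias sections (9.9, 9.12) do not mention this problem.

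**The concern.** The patients are the same before and after, but two features make the comparison unequal, and they push in opposite directions.

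- **Exposure.** The pre period cannot exceed 6 months. The post period lasts until treatment or data collection ends and will often be longer. More time at risk means more patients with at least one ADR.
- **Selection.** A patient usually enters this analysis because an ADR led to a reduction. If events are split by onset date, that ADR counts as pre. ADRs that tend to start early also fall there, whatever the dose. This step is inferred, because no counting rule is written, and it applies to reductions. Section 9.5 also expects escalations, to which it does not apply.

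A dose effect is added to both, and a crude percentage cannot separate the three. The risk is that a fall is read as confirming that reduction improves tolerability, or that a rise in some other ADR is read as harm, when neither reading is supported.

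**Working it through.** **Inputs from the documents.** LUX-Lung 3 reductions and pre/post percentages, and median PFS of 11.3 months in early reducers (section 7); the 6-month limit (section 9.7.1). All ADR rates, trigger probabilities and treatment lengths below are assumptions.

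**1. The precedent.** Section 7 says "dose reductions occurred in 53% (122/229) of patients; the majority (86%) within the first 6 months of treatment". Check: 122/229 = 53.3%. It lists 16 pre/post percentages, such as "99.2% (20.5%) to 46.7% (4.1%) for diarrhea". Of all denominators from 30 to 229, only 122 reproduces all 16 to one decimal: diarrhea 121/122 = 99.2% and 57/122 = 46.7%; nail effects 54/122 = 44.3% and 45/122 = 36.9%. The precedent is therefore plain patient percentages on the same 122 patients, with no visible exposure adjustment.

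**2. Exposure alone.** With constant rate λ per month, the share with at least one event in t months is 1 − exp(−λt). Assume 2 months pre and 9 months post.

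| λ | Pre | Post |
|---|---|---|
| 0.05 | 1 − exp(−0.10) = 10% | 1 − exp(−0.45) = 36% |
| 0.10 | 1 − exp(−0.20) = 18% | 1 − exp(−0.90) = 59% |
| 0.30 | 1 − exp(−0.60) = 45% | 1 − exp(−2.70) = 93% |

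The percentage rises although the rate is unchanged.

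**3. Trigger alone.** If one ADR is the only cause of reduction, its pre percentage is 100% by construction. At 5% per month with no dose effect, the post percentage is 1 − 0.95³ = 14%, 1 − 0.95⁶ = 27% or 1 − 0.95⁹ = 37% after 3, 6 or 9 months.

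**4. Both together, no dose effect.** For a sole-trigger ADR with constant rate λ and exponential treatment time of median M, the expected post percentage is λ/(λ + ln 2/M). With λ = 0.10: M = 11 gives 0.10/(0.10 + 0.063) = 61%; M = 6 gives 0.10/(0.10 + 0.116) = 46%. Both start from 100%.

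A simulation extended this to 90 scenarios of 150,000 patients each. It used λ of 0.1, 0.3 or 1.0; constant or early onset (cumulative intensity λt to the power 1, 0.5 or 0.25); median treatment of 6 or 11 months; and one ADR type, or four equally frequent types, with various trigger probabilities.

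- One ADR type driving all reductions: its percentage fell in 36 of 36 scenarios, by 6 to 91 points.
- Four competing types, constant rate: the percentage for one type fell in 0 of 18. Example: 36% to 61%, with mean exposure of 2.4 months pre and 15.8 months post.
- Four competing types, early onset: it fell in 17 of 36.

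**5. Do person-time rates repair it?** Not by themselves. Counting the trigger, the pre rate exceeded the post rate in 90 of 90 scenarios, for example 0.40 against 0.10 when the true rate is a constant 0.10. Removing the trigger, it did so in 36 of 90. In the four-type example of step 4, the true rate for all types together is 0.40 per month. The pre rate is 0.69 with the trigger and 0.28 without it; the post rate is 0.40. The first overstates a fall and the second over-corrects.

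**6. Date imputation.** The SAP's rule for incomplete AE onset dates uses the first-dose date whenever that date lies in the possible interval. Such ADRs move into the pre period.

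**The case against.** The safety analysis is declared descriptive, the comparison with LUX-Lung 3 is descriptive, and the checklist records that there is no prior hypothesis. A crude table in the precedent's format serves that comparison. This stands as a reason to keep the table. It does not settle how to read it, because the objective speaks of effects.

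A reader might infer that the percentages must fall even without a dose effect. The documents do not support that. Exposure pushes the other way, and a fall is certain only for an ADR that alone drives reductions.

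A reader might also take the 99.2% for diarrhea as proof that pre values are near 100% by selection. The other all-grade pre values are 88.5%, 77.0% and 44.3%, and no rate in non-reducers is given, so diarrhea may simply be very common. The 100% in step 3 is likewise no forecast. Section 7's grade 3 or higher pre values are 20.5%, 26.2%, 12.3% and 16.4%. They sum to 75.4%, so at least 24.6% of reducers had none of these four at that grade before reduction.

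Finally, absence is not fully established. The SAP announces tables, but only its derived variables are visible, and a contents entry after 9.7.1 is blacked out.

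**Conclusion.** The point holds as a cheap improvement. On the visible plan, the crude pre/post contrast can rise or fall with no dose effect, and the documents do not fix the net direction for a given ADR. For an ADR that alone drives reductions it falls, by 6 to 91 points in the scenarios examined. For one of several competing ADRs at a constant rate it rises. These sizes rest on assumed rates and treatment lengths, and the trigger part rests on splitting events by onset date and on reductions only.

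It would go too far to say that the study cannot address its primary safety question. A descriptive account remains possible; attributing a change to the dose from the crude table does not.

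**What to change.** Keep the crude table for the LUX-Lung 3 comparison. State in section 9.7.1 or the SAP how the two periods are defined and how prompting and ongoing ADRs are counted. For dose reductions, add:

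1. Patient-months at risk in each period and exposure-adjusted ADR incidence with 95% CI, with ADRs ongoing at the change in a separate row.
2. The same rates without the ADR recorded as the reason for modification, where the record allows that link.
3. Rates in matched windows of time since first dose in patients not modified, to show the natural decline of early-onset ADRs.

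Label all three as sensitivity analyses. None is unbiased: counting the trigger overstates a fall, removing it can over-correct, and unmodified patients may differ in tolerance. Flag ADRs whose onset was imputed to the first-dose date. Report the pre/post result as descriptive, and do not attribute a fall to dose reduction on the crude table alone. If such tables already exist, refer to them in section 9.7.1.

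Cost: a few tables from dates and reasons already collected under section 9.3. The rates assume a roughly constant hazard within each period, and the link from reason to ADR record may be incomplete.
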